### **2.2      Secondary Objectives**

A secondary objective of the study is to establish the feasibility of biochemical verification of smoking cessation in a fully remote, digital clinical trial. Concordance between self-reported abstinence and measurements of exhaled carbon monoxide (CO) at study outcome will be

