### **3. STUDY DESIGN**

#### **3.1 Overview of Study Design, Doses and Control Groups**

The overarching study aim is to recruit a population of current smokers who are motivated to quit with the assistance of a mobile solution, enroll them into a study testing apps to help them quit, and randomize them into one of two arms. The core study period will consist of 8 weeks of usage of Clickotine or QuitGuide. At the end of this period, users will receive notifications to link them to an online survey, which will record their responses in a secure database. The primary outcome is successful short-term quitting, measured by 30-day point prevalence abstinence (self-reported and confirmed with expired CO < 7ppm). This study includes rigorous methodological standards to address potential limitations inherent to digital and behavioral interventions. In implementing an effective active control in a hypothesis-blind manner, the study sets a particularly high bar for establishing superiority of CKT. However, the investigators find it essential to use this strong control in order to demonstrate clear evidence of effectiveness that will be understood as clinically meaningful by Magellan Health and other providers, payers, and regulatory agencies.

All subjects will be encouraged to submit a CO sample using an iCO Smokerlyzer device at Week 4 and Week 8 (study completion). The iCO Smokerlyzer device will be mailed to participants after study randomization. Week 4 CO assessment submission is a compliance check and only recorded as a data point of successful submission. The CO assessment will be conducted during the outcome assessment after the 8-week study period regardless of self-reported smoking status.

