## **7.2 Randomization**

Randomization to treatment arm will utilize a predetermined sequence for up to 195 participant enrolled in the study, balanced 1:1 CKT:QG, balanced in blocks of 4. The research coordinator will be the only study staff member with access to the randomization sequence and will assign participants to CKT or QG based on their position in the randomization sequence.

Randomization procedures will occur via telephone with the research coordinator to verify participant eligibility and confirm download of installed treatment arm application on the randomization date. In the case of technical error during the scheduled call or other need to reschedule, participants will have 1 business day to reschedule the randomization call with the research coordinator. If calls are not conducted within the protocol window, the participant will be considered a screen failure and not included in the ITT sample.

Participant study eligibility will be verified prior to randomization on the day of the scheduled telephone contact with the research coordinator. Once eligibility is confirmed, the research coordinator will facilitate randomization assignment into a treatment group of CKT or QG. The assigned treatment arm and Smokerlyzer application links will be emailed to the participant for downloading of CKT or QG.

The study intervention start **date/ day 0** will be on same day of randomization and confirmed installed treatment application of activated Clickotine or QuitGuide. Only randomized participants that are able to confirm download of assigned treatment arm will be included in the ITT sample.

In the event participants are randomized to a treatment group and unable to confirm successful download of assigned treatment application, they will be **excluded** from the study by (*Incl # 10*) and will **NOT** be included in the study ITT sample.

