#### **10.4 Secondary Endpoint**

Concordance rates between self-reported 30-day abstinence and the remote CO monitoring result will be estimated, with concordance > 85% considered evidence of a valid reporting process by Magellan Behavioral Health. Concordance rates will be compared between users that submit the CO measurement under video monitoring and those that do not. Upon completion of the Outcome Survey, participants will be invited to submit the CO assessment over a live video feed to confirm identity, until videos are received from 25 CKT users and 25 QG users. After 25 videos are received from each group, participants will no longer be invited to submit the CO assessment over live video feed.

Secondary analysis of the subgroup of NRT/pharmacotherapy users will be conducted to compare cessation rates between the CKT+NRT group and the CKT-only group, to confirm the initial trial result that CKT+NRT is not superior to CKT-alone.

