#### **10.5 Sample Size**

Power analysis: Estimated ITT 30-day cessation rates after 8-weeks of use for CKT and QG are based on published reports: CKT 26.2%, QG 8.3%. A power analysis for logistic regression using g\*Power 3.1 software was conducted with the following parameters: 85% power to detect a group difference with  $\alpha = 0.05$  two-sided significance level, and estimated Group 1 proportion,  $p_1$ , of 0.262 and a Group 2 proportion,  $p_2$ , of 0.083. A sample size of 78 subjects in each group will yield 85% power to detect such a difference. To obtain this sample size, we plan to obtain consent from 195 subjects and enroll 156 into the study by downloading the assigned app, which reflects a conservative approach to the retention rate observed in our pilot data.

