The purpose of this SBIR Phase 1 project is to demonstrate the efficacy of Clickotine (CKT) in producing long-term cigarette abstinence in a value-based care population served by Click Therapeutics, Inc.’s commercial partner Magellan Behavioral Health, and to demonstrate the ability to base reimbursement from CKT on remote biochemical verification of successful cigarette abstinence. To do so, this SBIR Phase 1 project will support a pilot blinded, randomized, controlled trial of CKT versus the NCI QuitGuide (QG) app to test the hypothesis that CKT will produce greater 30-day abstinence rates than QG after 8 weeks of use. To demonstrate the feasibility of evaluating CKT in a Magellan value-based care population, half the study sample will be recruited from a Magellan value-based care population. To demonstrate the ability to base reimbursement on remote biochemical verification of successful cigarette abstinence, concordance rates between self-reported cessation on the outcome survey and the exhaled CO monitor result will be investigated; video monitoring of a subset of the first 50 study completers (first 25 completers in both CKT and QG groups) submitting the exhaled CO assessment will be conducted to validate the remote CO monitoring process. Smokers that are currently using a pharmacotherapy or Nicotine Replacement Therapy (NRT, including e-cigarette use) at study enrollment will not be eligible to participate. However, since some users are expected to choose to begin using smoking cessation pharmacotherapy or NRT during their quit attempt, users will be permitted to begin using smoking cessation pharmacotherapy or NRT during the trial if they so choose. Secondary analysis of the subgroup of NRT/pharmacotherapy users will be conducted to compare cessation rates between the CKT+NRT group and the CKT-only group, to address expected med/NRT use during the trial and to confirm the initial trial result that CKT+NRT is not superior to CKT-alone.

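### The >85% concordance benchmark has no stated denominator or missing-CO rule and, read naturally, does not show whether abstinence claims are verified

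*Protocol*

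**What the plan says.** - **Benchmark.** Section 10.4 of the Protocol and of the SAP compares the self-reported 30-day status with the remote CO result, "with concordance > 85% considered evidence of a valid reporting process by Magellan Behavioral Health". It names no denominator, no confidence limit and no rule for a missing reading. The same rate is to be compared between participants who submit CO on video and those who do not.
- **Who gives CO.** Protocol 3.1: "The CO assessment will be conducted during the outcome assessment after the 8-week study period regardless of self-reported smoking status".
- **Purpose.** Protocol 2.2 aims to "establish the feasibility of biochemical verification of smoking cessation in a fully remote, digital clinical trial". The SAP (Data and Safety Monitoring Plan, Summary of the protocol) aims to "demonstrate the ability to base reimbursement from CKT on remote biochemical verification of successful cigarette abstinence".
- **Missing CO.** Protocol 8.2 treats a participant who lacks the survey or the CO reading as lost to follow-up. Protocol 7.11 applies that status only when the survey is missing. The SAP's Data Analysis Plan imputes non-response as smoking but does not say whether this covers CO.
- **Cut-off.** Abstinence by CO is below 7 ppm in Protocol 8.3 and 11.1, and below 8 ppm in the SAP's Data Acquisition text.

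**The concern.** Both stated purposes concern people who say they have quit: can their claim be checked remotely, and could a payer rely on the check? Overall agreement also counts everyone who says they still smoke, and at the planned quit rates they are the large majority. A figure above 85% may then say little about the claims themselves.

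Section 10.3 defines the primary endpoint by self-report alone, so concordance is the plan's main check on it. If the benchmark can pass or fail for reasons unrelated to the truth of the claims, the trial could misreport, in either direction, whether reporting is valid.

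**Working it through.** **The plan's own figure.** Neither document shows a calculation behind the 85% benchmark. The sample size supplies the quit rates used here, and it reproduces. Section 10.5 states: "A sample size of 78 subjects in each group will yield 85% power to detect such a difference". With p1 = 0.262, p2 = 0.083 and mean 0.1725, two-sided 5%, no continuity correction:

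n = [1.960 × √(2 × 0.1725 × 0.8275) + 1.036 × √(0.262 × 0.738 + 0.083 × 0.917)]² / 0.179² = 78.4, that is 79 per arm. Power at 78 per arm is 84.8%.

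**Inputs.** 78 per arm and the two quit rates (10.5); pilot retention 87.7% (Protocol 1.3), assumed equal in both arms. The CO submission rate is not in the documents and is varied below. A claim is called false here when its CO reading is at or above the cut-off.

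**Step 1: who is in the rate.**
- Abstinence claims: 78 × 0.262 + 78 × 0.083 = 20.4 + 6.5 = 26.9.
- Completers: 156 × 0.877 = 136.8.
- Admitted smokers: 136.8 − 26.9 = 109.9, and 109.9/136.8 = 80%.

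**Step 2: passing with false claims.** Let s be the share of admitted smokers reading at or above the cut-off and t the share of claims reading below it. The benchmark passes when (109.9s + 26.9t)/136.8 > 0.85.
- s = 1: t > 0.237, so up to 76% of claims can be false. In whole persons, 117/137 = 85.4% passes with 20 of 27 false.
- s = 0.95: t > 0.442, up to 56% false.
- s = 0.90: t > 0.646, up to 35% false.

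If all 27 were false, agreement would be 110/137 = 80.3% and the benchmark would fail. The passing result 117/137 has a Wilson 95% CI of 79% to 90%, which the plan does not ask for.

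**Step 3: failing with no false claims.** Among pilot completers 51.5% were 7-day and 29.9% 30-day abstinent (Protocol 1.3), a gap of 21.6 points. These people truthfully report smoking within 30 days. Assume they all read below the cut-off.
- CKT completers: agreement is 100 − 21.6 = 78.4% with every claim true.
- Pooled: the ITT gap is 45.2 − 26.2 = 19.0 points, so 78 × 0.19 = 14.8 CKT participants. The QuitGuide gap is not given. At 0, 5, 10 and 19 points, agreement over 137 is 89.2%, 86.3%, 83.5% and 78.4%.
- Room for false claims, out of the 20 discordant pairs allowed, is then 5 (gap 0), 1 (gap 5) or none (10 or more).

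**Step 4: does another denominator rescue it?** Entries are the smallest number of the 27 claims that must be verified to pass, taking all 110 admitted smokers as submitting and agreeing. The columns are assumed numbers of claimants who send CO.

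| Reading | 27 send CO | 20 send CO | 14 send CO |
|---|---|---|---|
| All with both measures | 7 (117/137 = 85.4%) | 1 (111/130 = 85.4%) | 0 (110/124 = 88.7%) |
| All 156, missing CO as smoking | 4 (133/156 = 85.3%) | 4 | 4 |
| Claimants with a reading | 23 (23/27 = 85.2%) | 18 (18/20 = 90.0%) | 12 (12/14 = 85.7%) |
| All claimants, missing as not verified | 23 (23/27 = 85.2%) | cannot pass | cannot pass |

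Only the last row ties a pass to a fixed, high number of verified claims.

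**The case against.** **The denominator is open.** Several passages speak of concordance with self-reported abstinence, which could mean claimants only. That stands as a matter of wording. The design points the other way. Video invitations go to anyone completing the survey until 25 videos arrive per arm, and concordance is compared across those submitters. The expected claims, 20.4 and 6.5, are below 25 in both arms, so a claimants-only rate does not fit the video plan.

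**A reader might infer that the plan drops abstainers who send no CO.** It does not say so. The lost-to-follow-up and non-response rules could make them discordant. The CO reading is paid for, chased by message and phone, and its compliance is reviewed monthly (Protocol 9.2). The gap is an absent rule, not a rule to exclude.

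**A reader might infer that the benchmark is simply too easy and would pass with most claims false.** That needs nearly every admitted smoker to read at or above the cut-off. The survey asks about any smoking in 30 days, while CO is a single reading. In the pilot, 21.6/70.1 = 31% of completers who had smoked within 30 days had not done so within 7. If they read below the cut-off, the benchmark is too hard. The direction of the error is not known.

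**A reader might infer that the arm with fewer quitters would be declared more valid.** Section 10.4 applies no benchmark by arm, so this is not a planned result.

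**It is only a secondary endpoint in a feasibility study.** This stands and limits the severity.

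**Conclusion.** The concern holds in this form: the >85% rule is under-defined, and on its natural reading it does not measure whether abstinence claims are verified. It can pass with up to about 20 of 27 claims false, and it can fail with none false. The first result assumes the planning rates, 87.7% retention in both arms, CO from all completers and full agreement among admitted smokers. The second assumes that truthful recent quitters read below the cut-off and, for the pooled rate, that QuitGuide has a gap of roughly 10 points or more.

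The documents do not support the claim that the benchmark will pass wrongly, nor that non-submitters are ignored by rule. The primary test as defined in 10.3 and the sample size are unaffected. Severity: should-fix.

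**What to change.** In 10.4 of both documents:

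1. Reconcile the 7 ppm and 8 ppm definitions first.
2. Define the validity measure as self-reported 30-day abstainers with a Week 8 CO below the cut-off, over all self-reported abstainers who completed the survey. Count a missing CO as not verified.
3. Judge the 85% benchmark on this proportion, with an exact or Wilson 95% CI. The threshold is attributed to Magellan, so confirm that it is meant for this quantity.
4. Report the CO submission rate among claimants, overall and by arm, as the feasibility result.
5. Keep overall agreement as descriptive, with its denominator stated, including for the video comparison.

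The cost is wording and one table; data collection does not change. The price is precision: with about 27 claimants, 23/27 = 85% has a Wilson 95% CI of 68% to 94%. The benchmark also becomes harder to meet, since it fails whenever fewer than 23 of 27 claimants send a reading. Reporting the submission rate beside it separates that failure from contradicted claims.

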## **1.2 Description of Clickotine®**

Clickotine® (CKT) is a novel app for iOS and Android smartphones, designed to provide smokers with essential features of the US Clinical Practice Guidelines (USCPG) for smoking cessation that are amenable to delivery via a mobile health solution (“the 5 A’s for smoking cessation”: advise/encourage to quit; assess willingness to quit and enhance motivation; assist with quit planning and connect with intervention- advice on pharmacotherapy, connect with counseling and medication treatments, provision of social support, and connect with a quit line; and arrange/provide follow-up) (Fiore et al., 2008).

Clickotine® embodies behavior modification Mechanisms of Action (MOAs) that have been supported by research: controlled breathing, personalized messaging, social engagement, treatment adherence, financial incentives, and digital diversions. These MOAs personalize cessation interventions to maximize effectiveness and user engagement. The MOAs are developed based on key features of clinical counseling services with advanced treatment personalization.

The controlled breathing Mechanism of Action provides a mindful breathing experience coupled with multisensory stimuli to reduce the negative symptoms of nicotine withdrawal, including cigarette craving and negative affect. This MOA was developed based on the works of multiple researchers, who demonstrated the effectiveness of controlled deep breathing on the severity of withdrawal symptoms (McClernon et. al, 2004; Shahab et. al, 2013; Westbrook et.al, 2013).

Personalized messaging involves sending customized text messages tailored to a user’s profile, specifically to their motivations and daily schedules. As a user spends more time engaging with Clickotine®, information is collected in the database and the messaging adjusts to be more effective. Numerous text messaging studies demonstrate significant efficacy in aiding quit journeys (Free et. al, 2011; Whittaker et. al, 2012).

Social engagement provides real-life support from friends, family and the community. Social engagement adds meaning to quit messaging (Richardson et al, 2013.), and helps users change their behavior through real-time support, cooperative quit planning and goal setting, and mutual motivation.

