## **2.      STUDY OBJECTIVES**

### **2.1      Primary Objective**

The primary objective is to confirm the improved efficacy of CKT for short-term smoking cessation through a blinded randomized controlled trial (RCT) vs. QuitGuide. Acceptance criteria: Self-reported 30-day point prevalence quit rates will be significantly higher in the CKT arm than QuitGuide.

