### **8.3 Assessment of Efficacy**

To assess 30-Day Sustained Abstinence from Smoking (NACQ, 2016) participants are asked the following questions in the Outcome Survey to determine Russell Standard Self- Reported 4-Week Quitter status (West et al., 2005):

1. Have you smoked (even a puff) in the last 30 days?

- a. Yes
- b. No

2. (If yes, this question will appear) Have you smoked (even a puff) in the last 14 days?
  - a. Yes
  - b. No
3. (If yes, this question will appear) Have you smoked (even a puff) in the last 7 days?
  - a. Yes
  - b. No

The Outcome Survey will instruct subjects to submit an exhaled carbon monoxide (CO) reading with the iCO Smokerlyzer they were mailed after participant randomization. iCO Smokerlyzer devices will be programmed to email the exhaled carbon monoxide measurement results to the research coordinator directly.

The primary outcome, 30-day abstinence from smoking, will be assessed via self-report on the outcome survey. Confirmation with the remote CO assessment will be conducted to assess concordance between self-report and remote CO assessment results. Abstinence as per the CO assessment will be defined as an iCO reading of fewer than 7ppm exhaled CO.

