### **10.3 Primary Endpoint**

The primary endpoint will be self-reported 30-day abstinence from smoking on the outcome survey as per Russell Standard Self- Reported 4-Week Quitter status.

30-day smoking cessation status (dichotomous variable: yes/no) will be compared between the CKT and QuitGuide groups utilizing logistic regression. Two-sided p-values will be calculated from logistic regression models, with adjustments to the models by: race, education, nicotine dependence, and living with a partner who smokes, consistent with previous studies' models.

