Primary outcome data, including covariates to be included in regression analyses, are acquired via the web-based baseline survey and outcome survey. Data are conveyed via an automated process from the web-based survey into a format matching the study database. Research coordinator is responsible for entering the survey data into the study database within 72 hours of survey completion.

Secondary outcome data: 1) CO readings are automatically conveyed via email by the iCO Smokerlyzer App to the study coordinator, who will enter the result into the database (a numerical value in parts-per-million (ppm; <8 ppm is defined as evidence of cigarette abstinence); 2) self-reported NRT and smoking cessation pharmacotherapy use (including e-cigarette use) will be acquired via the outcome survey.

Data Analysis Plan:

[name], will conduct all study analyses after the study database is locked. All analyses will be performed on the intent-to-treat (ITT) population, with non-response imputed as continued smoking. 30-day smoking cessation status (dichotomous variable: yes/no) will be compared between the CKT and QuitGuide groups utilizing logistic regression. Two-sided p-values will be calculated from logistic regression models, with adjustments to the models by: race, education, nicotine dependence, and living with a partner who smokes, consistent with previous studies' models.

Concordance rates between self-reported 30-day abstinence and the remote CO monitoring result will be estimated, with concordance > 85% considered evidence of a valid reporting process by Magellan Behavioral Health. Concordance rates between the video-monitored and unmonitored groups will be compared to determine the value of video monitoring the CO assessment.

Secondary analysis of the subgroup of NRT/pharmacotherapy users will be conducted to compare cessation rates between the CKT+NRT group and the CKT-only group, to confirm the initial trial result that CKT+NRT is not superior to CKT-alone.

Quality Assurance

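### The planned CO checks cannot show whether misreporting of abstinence differs between the randomised arms, although the primary comparison rests on self-report

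*Protocol*

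**What the plan says.** **Primary endpoint.** Protocol 10.3, repeated in SAP 10.3, states: "The primary endpoint will be self-reported 30-day abstinence from smoking on the outcome survey". The acceptance criterion in Protocol 2.1 agrees: "Self-reported 30-day point prevalence quit rates will be significantly higher in the CKT arm than QuitGuide". So does Protocol 8.3: "The primary outcome, 30-day abstinence from smoking, will be assessed via self-report on the outcome survey". The arms are compared by logistic regression.

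**CO data.** Protocol 3.1 has CO measured at the outcome assessment in both arms, whatever smoking status is reported.

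**Use of the CO data.** Two analyses are planned:
- A single concordance estimate, "with concordance > 85% considered evidence of a valid reporting process by Magellan Behavioral Health" (Protocol 10.4, SAP 10.4).
- A comparison by video status: "Concordance rates will be compared between users that submit the CO measurement under video monitoring and those that do not". The SAP's Data Analysis Plan says the same: "Concordance rates between the video-monitored and unmonitored groups will be compared to determine the value of video monitoring the CO assessment".

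The quota of 25 videos per arm fixes who is filmed; it is not an arm comparison. The hypothesis in Protocol 2.2 that groups will not differ in concordance follows directly on the video and non-video users just named.

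**A conflicting definition.** Protocol 3.1 describes the primary outcome as "30-day point prevalence abstinence (self-reported and confirmed with expired CO < 7ppm"). No statistical section contains an arm comparison of CO-confirmed abstinence.

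**The concern.** False abstinence claims made at the same rate in both arms mostly dilute a difference in self-reported quit rates. Claims that are less reliable in one arm than in the other feed directly into the primary odds ratio and can create or conceal an effect. The pooled concordance rate averages over the arms, and the video split mixes them, so neither can tell these two situations apart. The trial could meet its threshold for a valid reporting process while the primary difference was partly or wholly a difference in reporting.

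**Working it through.** **Inputs from the documents.** Planning rates 26.2% (CKT) and 8.3% (QG), 78 per arm, two-sided 0.05, 85% power (10.5 in both documents). Concordance threshold above 85% (10.4). Pilot retention 87.7% (Protocol 1.3). Non-response imputed as continued smoking (SAP, Data Analysis Plan). The documents give no false-claim rate, so every such rate below is an assumption.

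**Step 1: the plan's own figure.** The pooled two-proportion formula without continuity correction gives 79 per arm for 85% power, and 84.8% power at 78. The stated 78 is reproduced within rounding.

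**Step 2: the planned effect in people.** 78 × 0.262 = 20.4 and 78 × 0.083 = 6.5, a difference of 78 × 0.179 ≈ 14.

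**Step 3: can the pooled criterion pass when the whole effect is misreporting?** Suppose 6 true abstainers in each arm, false claims only in CKT, CO from all 156, and CO correctly identifying every claim. Tests are unadjusted.

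| False claims, CKT only | Self-report, CKT vs QG | Chi-square p | Fisher p | Pooled concordance | CKT concordance | QG concordance |
|---|---|---|---|---|---|---|
| 8 | 14/78 vs 6/78 | 0.055 | 0.092 | 148/156 = 94.9% | 70/78 = 89.7% | 100% |
| 9 | 15/78 vs 6/78 | 0.035 | 0.059 | 147/156 = 94.2% | 69/78 = 88.5% | 100% |
| 14 | 20/78 vs 6/78 | 0.003 | 0.005 | 142/156 = 91.0% | 64/78 = 82.1% | 100% |

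The pooled rate stays above 85% with up to 23 discordant participants of 156 (133/156 = 85.3%), more than the 14 that make up the planned effect. If only 68 per arm submit CO (78 × 0.877 ≈ 68) and all 14 false claimants are among them, the last row becomes 122/136 = 89.7% pooled and 54/68 = 79.4% in CKT. The pooled criterion still passes.

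**Step 4: illustration of the false-positive risk.** Assume no true effect, with 8.3% abstinent in both arms. Let f be the excess false-claim rate among CKT smokers who can make a claim.
- Everyone responds: CKT claim rate = 0.083 + 0.917f.
- 87.7% respond in both arms, and all true abstainers are among them: responding smokers are 0.877 − 0.083 = 0.794 of the arm, so the rate is 0.083 + 0.794f.

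Exact binomial enumeration at 78 per arm, score test, probability of a significant result with CKT higher:

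| Assumed f | 87.7% respond | Everyone responds |
|---|---|---|
| 3% | 7.4% | 8.5% |
| 5% | 12.7% | 15.2% |
| 10% | 33% | 41% |

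The nominal figure in that direction is about 2.5%. The 87.7% column is the closer match to the plan, because a non-responder is counted as smoking and cannot make a false claim.

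**Step 5: what a by-arm table could show.** With about 20 claims in CKT and 6 in QG, precision is poor. If none of 6 QG claims is contradicted, the exact 95% interval for the contradicted share is 0% to 46%. For overall agreement near 90%, the half-width of a 95% interval for the arm difference is 1.96 × √(2 × 0.9 × 0.1 / n), or 9.4 points at n = 78 and 10.1 at n = 68.

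**The case against.** **Nothing shows that misreporting would favour CKT.** A reader might infer it from the feature list for Clickotine in Protocol 1.2 ("personalized messaging, social engagement, treatment adherence, financial incentives, and digital diversions") set against the short description of QuitGuide in 5.2. The documents do not support that step. No passage links app features to false claims, and the silence of a three-sentence description is not evidence that a feature is absent. Both apps are said to follow the same US guideline. The administrative letter says the trial moved to CT-101-M without listing which features that version kept. Study payments do not depend on quit status. Participants are hypothesis-blind (5.4) and the sponsor is masked (5.5). This stands: the direction is unknown and the risk is reduced. Blinding is a reason to expect balance, though, and does not test for it.

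**Protocol 3.1 already requires CO confirmation.** If that definition governed, a claim contradicted by CO would not count as abstinence in either arm and the problem would largely go. But it conflicts with Protocol 2.1, 8.3 and 10.3 and with SAP 10.3, and no analysis implements it. The conflict has to be settled first.

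**The bias would not be invisible.** A reader might infer that it could never be found. Paired CO and self-report data will exist in both arms, so a by-arm table could be made at any time. What is missing is the prespecified analysis.

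**The check is weak.** Also true, as Step 5 shows. That argues for estimates with intervals rather than a test; it does not argue for leaving the data unused.

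**Conclusion.** The gap is real and appears in both documents: CO is never applied to the randomised comparison in any planned analysis, and the two planned concordance analyses cannot reveal a difference in misreporting between arms. The worked example shows that the whole 17.9-point planned effect could be produced by false claims in one arm with pooled concordance at 91%. That example assumes 6 true abstainers per arm, complete CO, and error confined to CKT. The 7%, 13% and 33% probabilities are illustrations at assumed rates of 3%, 5% and 10%, under equal 87.7% response and unadjusted tests; they are not forecasts. The conclusion is that the plan does not check for differential misreporting, not that such misreporting is expected or that it would run in CKT's favour. This is a worthwhile improvement to the analysis plan and leaves the sample size unchanged.

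**What to change.** **Reconcile first.** Settle whether the primary outcome is self-reported (Protocol 2.1, 8.3, 10.3; SAP 10.3) or CO-confirmed (Protocol 3.1). Settle one CO cut-off: Protocol 3.1, 8.3 and 11.1 use below 7 ppm, and the SAP's Data Acquisition section uses below 8 ppm. Until then a contradicted claim has no single definition.

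**Then add to 10.4 in both documents and to the SAP's Data Analysis Plan:**
1. By randomised arm, with exact 95% confidence intervals and no significance test: agreement between self-report and CO; the proportion of abstinence claims contradicted by CO; and the proportion of claims with no CO reading.
2. A sensitivity analysis repeating the primary comparison with CO-contradicted claims recoded as smoking, run twice: missing CO left as self-reported, and missing CO counted as not abstinent. Both are needed because CO is submitted separately after the survey. Under the first rule alone, a false claim survives if no reading is sent.

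Keep the video comparison as planned.

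**Cost.** A few sentences and a small set of tables from data already being collected. The downside is imprecision: with about 20 and 6 expected claims, similar figures in the two arms must not be read as proof of equal reporting, and the text should say so.
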